### 6.3.3 Prior Medications and Procedures

Prior and concomitant medications will be coded using the WHO Drug dictionary.

Prior and concomitant medications and procedures will be summarized for the SAF set. Results for prior medications will be presented for each treatment group and overall, by Anatomic Therapeutic Class (ATC) level term 1, ATC level 3 and generic term.

Prior medications will be defined as any medication with a start date/time before the date/time of first dose of IMP. Refer to section 6.2.7.2 for partial or missing date rules).

If the end date is after the end of study date, end date will be imputed to end of study date.

Prior concomitant procedures will also be summarized and provided in a listing.

### 6.3.4 Concomitant Medications and Procedures

All concomitant evaluations will be summarized for the SAF set during the DBTP.

Medications (or procedure) with a start date/time on or after the date/time of first dose of IMP will be considered concomitant. Medications (or procedures) taken prior to the first dose of IMP and continuing after the first dose of IMP will be considered both prior and concomitant. All medications starting or ongoing during the DBTP are concomitant to this period. All medications starting or ongoing during the SFU period are concomitant to this period.

If a medication (or procedure) date is missing, or partially missing, and it cannot be determined whether it was taken on or after start of treatment, it will be considered a concomitant medication (or procedure). Refer to section 6.2.7.2 for partial or missing date rules).

If the end date is after the end of study date, end date will be imputed to end of study date.

Results for concomitant medications will be tabulated by ATC level 1, ATC level 3 and generic term for the DBTP period.

The use of concomitant medications and procedures will be included in by-participant data listing.

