### 1.2 Objectives

The objectives of the study ARGX-117-2002, as stated in the protocol, are:

Primary objective:

[figure not shown]
- To evaluate the safety and tolerability of ARGX-117 compared with placebo in adult participants previously stabilized with IVIg. The primary endpoints are adverse events (AEs), clinical laboratory variables, vital signs, concomitant medications, and suicidal behavior

Secondary objectives:

- To evaluate the efficacy of ARGX-117 compared with placebo on muscle strength and/or motor function in adult participants previously stabilized with IVIg based on:
  - Time to the first retreatment with IVIg since the final IVIg treatment of the IVIg monitoring period
  - Time to relapse
  - Modified Medical Research Council (mMRC) score that evaluate motor strength/weakness from predetermined muscle groups assessments
  - Grip strength (GS) assessments
- To evaluate the efficacy of ARGX-117 on functional ability, arm and hand function, quality of life, and fatigue in adult participants with MMN
- To evaluate the effect of ARGX-117 on health-related productivity and work productivity using Health-Related Productivity Questionnaire (HRPQ)
- To evaluate treatment satisfaction
- To assess the PK, PD, and immunogenicity of ARGX-117

Exploratory objectives:

[REDACTED]

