### 3 STUDY ENDPOINTS

#### 3.1 Primary Endpoints

Safety variables include AEs, clinical laboratory variables, vital signs and suicidal behavior.

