#### 6.2.7.2 Prior and concomitant medications missing dates

Medications and procedures administered will be classified by period of use as prior, concomitant or both prior and concomitant to IMP therapy. In the event of partial dates, the available date information will be used to categorize the initiation period accordingly. In the event that the classification is ambiguous, including for cases of completely missing dates, the medication will be assumed to be both prior and concomitant unless indicated as prior only due to the given stop date.

The following date imputation rules for partially missing dates reflect the above convention:

1. End date: Missing day will be imputed as the last day of the month, and missing month will be imputed by December, if not resulting in a date later than the date of the participant's death, date of study discontinuation or date of study completion. In the latter case, the date of death/date of study discontinuation/ date of study completion will be used to impute the incomplete end date.
2. Start date: Missing day will be imputed as the first day of the month, and missing month will be imputed by January.
3. If the start date is completely missing, then:
  - a. If the end date is prior to the date of first administration of the IMP, then the medication is considered as prior
  - b. If the end date is prior to the date of last administration of the IMP, then the medication is considered as prior and concomitant
  - c. If the end date is completely missing or after the date of last administration of the IMP, then the medication is considered as prior and concomitant.

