## 9.2 List of Tables, Figures and Listings

### 9.2.1 Tables and Figures

**Table 24 List of Tables and Figures**

TABLE/ FIGURE	NUMBER	TITLE	Interim Analysis 1 (cohort 1)	Interim Analysis 2 (cohort 1 + cohort 2)	Final analysis (cohort 1 + cohort 2)
GENERAL CHARACTERISTICS					
Table	14.1.1	Overall Disposition - Enrolled Set	x	x	x
Table	14.1.2	Overall Disposition - Safety Set	x	x	x
Table	14.1.3	Participants Disposition - by Country and Site - Enrolled Set	x	x	x
Table	14.1.4	Participants Disposition by Country and Site - Safety Set	x	x	x
Table	14.1.5	Study Periods Duration - Safety Analysis Set	x	x	x
Table	14.1.6	Protocol Deviations - Safety Set		x	x
Table	14.1.7	Overview of Analysis Sets - Enrolled Set	x	x	x

Table	14.1.8	Demographic and Baseline Characteristics - Safety Set	x	x	x
Table	14.1.9	Medical History - Safety Set		x	x
Table	14.1.10	MMN Disease History - Safety Set	x	x	x
Table	14.1.11	Confirmation of Diagnosis and IVIg Dependency by MCC - Safety Set	x	x	x
Table	14.1.12	IVIg History - Safety Set	x	x	x
Table	14.1.13	IVIg Treatment during IVMP - Safety Set	x	x	x
Table	14.1.14	Prior Medications - Safety Set		x	x
Table	14.1.15	Prior Procedures - Safety Set		x	x
Table	14.1.16	Summary of concomitant medications during DBTP - Safety Set		x	x
Table	14.1.17	Summary of concomitant procedures during DBTP - Safety Set		x	x
Table	14.1.18	IMP Exposure and Compliance - Safety Set		x	x
Table	14.1.19	Summary of DBTP Baseline Scores for Efficacy Endpoints		x	x
EFFICACY					
Table	14.2.1.1	Time to First Retreatment with IVIg during DBTP [1] - Safety Set	x	x	x

Figure	14.2.1.2	Time to First Retreatment with IVIg - Safety Set	x	x	x
Table	14.2.1.3	Time to Relapse during DBTP - Safety Set	x	x	x
Figure	14.2.1.4	Time to Relapse during DBTP - Safety Set	x	x	x
Table	14.2.1.5	Retreatment with IVIg during the DBTP - Safety Set	x	x	x
Table	14.2.1.6	Retreatment with IVIg Status according to Worsening status during DBTP - Safety Set	x	x	x
Table	14.2.1.7	Retreatment with IVIg Status according to Worsening status during DBTP - Safety Set	x	x	x
Table	14.2.1.8	Summary of mMRC-10 Sum Score during IVMP and DBTP - Safety Set	x	x	x
Table	14.2.1.9	Summary of mMRC-10 Sum Score during IVMP and DBTP by IVIg Dose Frequency Subgroup - Safety Set	x	x	x
Table	14.2.1.10	mMRC-10 Sum Score during DBTP - Analysis of Covariance - Trial-product strategy [1] - Safety Set	x	x	x

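### The concomitant-medication and procedure tables merge items started on treatment with items carried over, and SAP 1.2 and 3.1 disagree on whether medication use is a primary endpoint

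*SAP*

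**What the plan says.** **Status of the endpoint.** Section 1.2, under the primary objective: "The primary endpoints are adverse events (AEs), clinical laboratory variables, vital signs, concomitant medications, and suicidal behavior". Section 3.1, Primary Endpoints: "Safety variables include AEs, clinical laboratory variables, vital signs and suicidal behavior". Concomitant medication is in the first list and not in the second.

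**What is counted.** Section 6.3.4: "All medications starting or ongoing during the DBTP are concomitant to this period". The same section says that a drug taken before the first dose and "continuing after the first dose of IMP will be considered both prior and concomitant". Section 6.2.7.2 likewise has medications and procedures "classified by period of use as prior, concomitant or both prior and concomitant to IMP therapy". Section 6.3.3 adds: "Prior medications will be defined as any medication with a start date/time before the date/time of first dose of IMP".

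**What is produced.** The results are tabulated for the DBTP by ATC level 1, ATC level 3 and generic term. Table 24 lists one medication output for the period, 14.1.16, "Summary of concomitant medications during DBTP - Safety Set", and the matching procedures table, 14.1.17. Both are marked for interim analysis 2 and the final analysis. A by-participant listing of concomitant medications (16.2.4.8) is marked for interim analysis 1 and the final analysis.

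**The concern.** Medication use can reveal an effect of treatment only through what is started after the first dose. What participants already take at that point is a baseline characteristic. The SAP applies this logic to its other safety variables: adverse events count from the first IMP administration, and laboratory values and vital signs have treatment-emergent rules relative to baseline. Concomitant medication has no equivalent, although the text already distinguishes the two kinds of use.

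At stake is whether a variable that section 1.2 calls primary can show a difference in drugs newly needed on ARGX-117. In rows where many participants already use something in the class, much of such a difference would disappear from the table, and chance differences in background use would be added to it.

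**Working it through.** The SAP states no figure for medication use, so there is none to reproduce. The check is textual, followed by an illustration.

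**1. Can new starts be recovered from other planned tables?** No. The prior-medication table (14.1.14) cannot be subtracted from 14.1.16. Under section 6.3.3 it also holds drugs stopped before the first dose, and one participant can appear in both tables.

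**2. How much is diluted?** Assumptions: each participant counts once per row; a share b in both arms already uses something in the row at first dose; among the others, shares p1 (ARGX-117) and p0 (placebo) start something.

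- Merged row: m = b + (1-b)p
- Difference shown: m1 - m0 = (1-b)(p1 - p0)

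The fraction retained, 1-b, does not depend on p1 or p0. Sizes: 24 per cohort at 2:1 gives 16 active and 8 placebo (cohort 1, and cohort 2 under option 1 or 2). The standard error is √[m1(1-m1)/16 + m0(1-m0)/8]. With p1 = 40% and p0 = 10%, both assumed:

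| b | ARGX-117 row | Placebo row | Difference (points) | SE (points) | Difference / SE |
|---|---|---|---|---|---|
| 0% (new starts only) | 40% | 10% | 30 | 16.2 | 1.85 |
| 5% | 43% | 14.5% | 28.5 | 17.6 | 1.62 |
| 10% | 46% | 19% | 27 | 18.6 | 1.45 |
| 25% | 55% | 32.5% | 22.5 | 20.7 | 1.09 |
| 50% | 70% | 55% | 15 | 21.0 | 0.71 |
| 75% | 85% | 77.5% | 7.5 | 17.3 | 0.43 |
| 90% | 94% | 91% | 3 | 11.7 | 0.26 |

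Against the pooled placebo column (16 v 16) the SE is 14.4 points at b = 0 and 16.9 at b = 50%, so the ratio falls from 30/14.4 = 2.08 to 15/16.9 = 0.89. The ratio is a gauge of readability, not a test.

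**3. Which rows are affected?** ATC level 1 contains level 3, which contains the generic terms, so b cannot fall on moving up to a broader row. Dilution is greatest in broad classes. It may be trivial for a generic term that few participants take at baseline.

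**4. Would splitting on the existing classification work as it stands?** Not fully. Section 6.2.7.2 imputes a missing start day as the first of the month and a missing month as January, and classes ambiguous cases as both prior and concomitant. A drug started later in the month of first dose, with the day missing, would normally be dated before that dose. Section 6.3.4 describes undeterminable cases simply as concomitant. The adverse-event rule in 6.2.7.1 goes the other way: a missing day in the month of first dose becomes the day of first dose.

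**The case against.** The merged definition is coherent. It describes all drug exposure in the period, and the table does what its title says. That stands: the definition is not an error, and what is missing is a breakdown.

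Primary status is not carried through. Section 3.1 omits the variable, the analysis sits under study population rather than safety, and the tables are grouped with general characteristics. Section 1.2 repeats objectives from a protocol not seen here, and section 7 is partly redacted. So primary status cannot be treated as settled; the conflict itself is the point.

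New use is visible elsewhere. IVIg retreatment has its own summaries of participants, administrations, dose and interval. Grade 3 or higher infections, hypersensitivity, anaphylactic and local reactions are tabulated as treatment-emergent events. In about 48 participants a listing can be read in full. This reduces the risk but does not remove it. A listing gives no rate by arm, and 16.2.4.8, like almost every listing, is not marked for interim analysis 2, where the merged table is. Event tables show events, not the drugs given.

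A reader might go further and infer that the table mainly shows baseline therapy, or that medication use cannot inform safety at all. The SAP supports neither. It gives no background rates, and rows with low background lose little. An overall row for any medication, where dilution would be worst, is not among the levels section 6.3.4 names.

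**Conclusion.** The point holds as a missing breakdown together with an inconsistency. Sections 1.2 and 3.1 conflict on endpoint status, and the only DBTP summaries of medications and procedures merge carried-over with newly started items. The loss is a factor (1-b) on any difference in new use: a tenth is lost at b = 10%, half at 50%, nine tenths at 90%. This rests on equal background use in the arms and on new starts counted among those without background use in the row; b is unknown. The 40% and 10% rates only illustrate. The trial is descriptive, so no alpha, power or sample-size figure is affected. This is an inexpensive improvement that should be made, not an error that invalidates an analysis.

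**What to change.** - In Tables 14.1.16 and 14.1.17 show, by arm: (a) items with start date/time on or after the first IMP dose; (b) items ongoing at the first dose.
- State how partial or missing start dates are assigned, and align 6.2.7.2 with 6.3.4. One option is a separate row for items whose dates do not settle the matter, so that new starts are not moved silently into (b).
- Reconcile sections 1.2 and 3.1 on whether concomitant medication is a primary endpoint.

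The cost is SAP wording and a split of two planned tables using start dates already needed for the classification. The downside is longer tables.

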### 6.3.5 Exposure and Compliance

Exposure and compliance of ARGX-117 and Placebo will be summarized in SAF set for each cohort.

Summary statistics of duration of treatment (weeks), number of infusions, duration for the first infusion (min), dose for the first infusion (mg/kg), average duration for subsequent infusions (min), average dose for the subsequent infusions (mg/kg) and cumulative dose (mg/kg) will be presented.

Duration of treatment (days) will be defined as (Last Dose Date – Start Dose Date + 1)/7.

Dose (mg) is calculated as volume of IMP (collected in CRF) multiplied by strength (mg/mL). Dose (mg/kg) is calculated by dose divided by weight in kg at baseline.

For cohort 2, in the case of selection of dose regimen 3, for participants who received active treatment, administrations of placebo will be taken into account in the calculation of the dose related parameters (number of infusions, average duration for subsequent infusions, average dose for the subsequent infusions and cumulative dose)

Compliance will be derived as follows:

$$\text{Compliance (\%)} = \frac{\text{Number of doses received}}{\text{Number of expected doses}} \times 100$$

Where the number of doses expected is the number of planned doses up to v14 (D113) or early treatment discontinuation visit (if a participant withdraws during the DBTP). In practice, all possible planned visits, including the potentially missed visits, up to the last planned visit in the DBTP of the participant available in the database, will be used as the denominator.

IMP exposure and compliance will be listed.

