**Double Blind Treatment Period (DBTP):**

- For the efficacy endpoints: From the first IMP administration date/time to V14 with 23:59 added as time part or date of early treatment discontinuation visit with 23:59 added as time part
- For AE and concomitant medication: From the first IMP administration date/time to:
  - Informed consent of LTE for participants who do enter into LTE. Date of informed consent corresponds to the treatment completion date in the main study. All data on the eCRF will be considered to belong to this period
  - 23h59 the day prior to the 1st FU visit at week 4 for those participants who do not enter into LTE or date of early study discontinuation with 23:59 added as time part if participant discontinued the study before FUV1
  - Date of study discontinuation with 23:59 added for participants who early discontinued study and do not enter in the safety follow up period

**DBTP and Safety Follow-up period:** For AE, from the first IMP administration date/time to:

- Informed consent of LTE for participants who do enter into LTE. Date of informed consent corresponds to the treatment completion/discontinuation date. All data on the eCRF will be considered to belong to this period
- Study discontinuation for those participants who do not enter into LTE

Participants who entered into LTE are participants who were eligible for LTE and signed the informed consent form.

**Study Day 1 IDVP:** The day of the first IVIg administration during IDVP

**Study Day 1 IVMP:** The day of the first IVIg administration during IVMP

**Study Day 1:** The day of the first administration of ARGX-117 or placebo

**Study Day 1 FU:** The day following V14/ED visit (D113) (for participants who do not enter into the LTE)

**End of Treatment Visit:** The V14 visit (D113) for participants who completed DBTP, or the visit following IMP discontinuation for participants who discontinue IMP prior to V14 (D113) or the last IMP administration date for participants who are on-going in the DBTP at the data cut-off date .

**End of Study Visit:** The V14 visit (D113) for participants entering the LTE, or the last recorded date in the DBTP or SFU period for participants not entering the LTE.

Scheduled or Unscheduled visits which do not fall into the visit windows will be listed, but not included in tables or graphs.

- **Conversion factors:**
  - 1 month = 30.4375 days
  - 1 year = 365.25 days
  - 1 week = 7 days
  - °C = (°F - 32)/1.8
- **Additional rules**

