**Table 16 PK Parameters**

Parameter (Units)	CDISC TERM	Definition	Method of Determination
AUC 0-72h  AUC 0-168h  AUC 0-336h	AUCINT	Area under the concentration versus time curve from 0 to 72 ,0 to 168 h, 0 to 336 h	Calculated using the linear up/log down variant of the trapezoidal rule
C max	C MAX	maximum observed serum concentration	Observed value
C 72h  & C 168h 	C MAX	concentration at 72 h for every week and 168 h for every 2-week dosing after dosing	Observed value
T max	T MAX	time to reach C max	Observed value

[REDACTED]

[REDACTED]

[REDACTED]

[REDACTED]

[REDACTED]

All serum concentration data a will be displayed in listings.

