9-HPT=9-Hole peg test; ANA=anti-nuclear antibody; BMI=body mass index; CAP-PRI=chronic acquired polyneuropathy patient-reported index; C-SSRS=Columbia suicide severity rating scale; dsDNA=double stranded DNA; DBTP=double-blinded treatment period; ECG=electrocardiogram; ENA=extractable nuclear antigen antibodies; ED=early discontinuation; EQ-5D-5L= Euro-Quality of Life 5 Dimensions 5 Levels; FSS=fatigue severity scale; HRPQ=health-related productivity questionnaire; IMP=investigational medicinal product; IMV=IVIg monitoring visit; INR=international normalized ratio; IV= intravenous; IVIg=intravenous immunoglobulin; LTE=long-term extension; MMN=multifocal motor neuropathy; MMN-RODS=Rasch-built overall disability scale for MMN; mMRC=modified Medical Research Council; NAb=neutralizing antibodies; ██████████ PD=pharmacodynamic(s); PE=physical examination; PGIC=patient global impression change; PHQ-9=patient health questionnaire 9 depression questionnaire; PK=pharmacokinetic(s); SIB=suicidal ideation and behavior; SLE=systemic lupus erythematosus; TSQM=Treatment Satisfaction 14-item Questionnaire for Medication; UNS=unscheduled; V=visit

Note: Participants who do not elect to enroll in the long-term extension study will have additional follow-up visits described in Table 3

Note: All assessments will be performed before IMP or IVIg administration unless otherwise specified.

Note: V1 will be 7 days after the final day of IVIg administration for IMV3 (Table 1)

\* For Germany only: A SARS-CoV-2 rapid antigen test must be completed or a negative rapid antigen test not older than 48 hours (depending on local requirements) must be presented upon site entry for each visit. The antigen test must be negative before the visit can begin. Rapid antigen testing will only be mandatory if required locally.

- a [REDACTED]
- b The assessments in this visit are for participants who complete the DBTP and participants who discontinue prematurely after randomization (ie, ED visit). The activities and assessments for the participants who roll over to the LTE will be provided in the ARGX-117-2003 LTE protocol.

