- c Participants who demonstrate a clinical deterioration during the DBTP may be re-treated with IVIg. A UNS IVIg visit will be performed at the participant's first occurrence of clinical deterioration necessitating retreatment with IVIg. If the timing for subsequent IVIg retreatment does not coincide with a regularly scheduled visit day of the DBTP, a UNS visit will be performed for the participant to receive IVIg.
- d A UNS visit can occur at the request of the investigator and additional assessments can be performed at the discretion of investigator. (X) indicates that the assessment will be performed at the discretion of the investigator.
- e A urine pregnancy test will be performed at V1, V6, V8, V11, V12, V14/ED and at any UNS visits for women of childbearing potential.
- f The PE will include the parameters specified in Section 8.2.1 of the protocol.
- g The weight measured at IMV3 will be used to calculate the dose for all IMP administrations.
- h Triplicate 12-lead ECGs will be performed during screening and at V1. A single 12-lead ECG will be performed at all other scheduled time points.
- i The C-SSRS will be used to assess the risk of suicidal ideation at screening. SIB risk monitoring will be based on question 9 of the PHQ-9 at all other scheduled time points.
- j An ANA test will be performed at the specified time points, the titer and staining pattern will be reported; the potential presence of ENA autoantibodies (anti-dsDNA, anti-Smith, anti-phospholipid (anti-cardiolipin IgG and anti-beta-2-glycoprotein IgG), anti-Ro (anti-Ro52 and anti-Ro60), anti-La and anti-U1RNP) will be evaluated from the blood samples collected. The presence of ENA autoantibodies will only be reported if ANA  $\geq$ 1:100.
- k PK and PD assessments on day 1 will be performed predose, 2 hours, and 6 hours postdose of the IMP infusion. Detailed schedules for collecting blood samples for PK and PD analyses are provided in Table 4 and Table 5.
- l A detailed schedule for collecting blood samples for cytokine analyses is provided in [Table 23](#).
- m Immunogenicity assessments will be performed predose of IMP administration.
- n [REDACTED]
- o Sample collection is optional.
- p Samples must be collected predose on days when IMP or IVIg are administered.
- q IVIg will be administered to participants demonstrating a meaningful clinical deterioration.

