**Table 21 Blood Collection Schedule for PK and PD Analyses**

The table content is redacted with a large black box.

IMP=investigational medicinal product; PD=pharmacodynamic; PK=pharmacokinetic; V=visit

- a Day 4 (V2) is not mandatory and is considered an optional visit. A minimum of 14 participants per cohort are targeted to attend the optional visits.
- b Blood samples will be collected from the participant before the start of the IMP administration.
- c The timing of postdose sample collection is relative to the start of the IMP infusion.
- d Blood samples will be collected immediately at the end of the infusion.

[REDACTED]

[REDACTED]

[REDACTED]

[REDACTED]

[REDACTED]

[illegible]

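### The compliance formula divides by expected doses, but the rule for computing it counts planned visits, so a fully dosed participant would score below 100%

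*SAP*

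**What the plan says.** Section 6.3.5 gives compliance as the number of doses received divided by the number of expected doses, times 100. The first sentence after the formula keeps to doses: "Where the number of doses expected is the number of planned doses up to v14 (D113) or early treatment discontinuation visit". The next sentence says how this will be computed in practice and changes the unit. The denominator becomes "all possible planned visits, including the potentially missed visits, up to the last planned visit in the DBTP" that is available for the participant in the database. Nothing limits this to visits with a scheduled infusion.

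Other parts of the SAP bear on whether every visit is a dosing visit:

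- Table 21, footnote a: "Day 4 (V2) is not mandatory and is considered an optional visit".
- Section 5.2, definition of the End of Treatment Visit: "The V14 visit (D113) for participants who completed DBTP". For participants who stop IMP earlier, it is the visit that follows the stop.
- Table 19, footnote b, on the V14/ED column: "The assessments in this visit are for participants who complete the DBTP and participants who discontinue prematurely after randomization (ie, ED visit".
- Table 16 describes the timed concentrations as "concentration at 72 h for every week and 168 h for every 2-week dosing after dosing".

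**The concern.** The numerator counts infusions and the operational denominator counts visits. A programmer will follow the practical instruction, not the sentence before it. Under that instruction, each planned visit without a scheduled infusion adds one to the denominator and can add nothing to the numerator. A participant who received everything that was planned then appears partly non-compliant.

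The primary objective is safety and tolerability, and the exposure and compliance table tells the reader how much of the planned treatment stands behind the safety results. A percentage that cannot reach 100% gives the wrong message there.

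**Working it through.** The SAP states no compliance figure, so there is nothing to reproduce. The check asks what the literal rule gives for a participant who missed no dose.

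**Inputs**

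- *Planned visits: 14.* The rows of Table 19 are read as V1 to V14/ED plus two columns for unscheduled visits. The pregnancy-test row confirms this, because its marks fall where footnote e puts them: "A urine pregnancy test will be performed at V1, V6, V8, V11, V12, V14/ED", plus unscheduled visits.
- *V2 is probably not a dosing visit.* It falls on day 4, three days (72 h) after day 1. Table 16 has a 72 h concentration and speaks of weekly and two-weekly dosing. The footnote that makes V2 optional belongs to the blood-sampling table, and it adds: "A minimum of 14 participants per cohort are targeted to attend the optional visits". A required infusion does not fit an optional visit.
- *V14 is probably not a dosing visit.* It closes treatment for completers, and the same column serves participants who have already discontinued.
- *Number of non-dosing visits, k.* This is an assumption, because the IMP row of Table 19 and the regimen definitions are redacted or missing.

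**Formulas for a fully dosed completer**

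- Literal rule: 100 × (14 − k) / 14
- Definition by planned doses: 100 × (14 − k) / (14 − k) = 100%

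| Visits without an infusion | k | Literal rule | By planned doses |
|---|---|---|---|
| none | 0 | 14/14 = 100.0% | 100% |
| V2 only, or V14 only | 1 | 13/14 = 92.9% | 100% |
| V2 and V14 | 2 | 12/14 = 85.7% | 100% |

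The last row has the best support in the visible text. Larger k would lower the figure further, but nothing visible identifies further non-dosing visits.

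**One missed dose, with k = 2**

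- Literal rule: 11/14 = 78.6%
- By planned doses: 11/12 = 91.7%

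**Early stop, V2 non-dosing, every dose up to the last visit received**

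- Last planned visit V3: 2/3 = 66.7%
- Last planned visit V4: 3/4 = 75.0%
- By planned doses: 100% in both cases

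The shortfall is therefore larger for participants who stop early, because one extra visit weighs more in a short denominator.

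**The case against.** The strongest defence is that the practical sentence only implements the definition before it. In a paragraph about IMP compliance, planned visits may simply mean planned dosing visits. The sentence would then do no more than say that missed occasions count and that counting stops at the participant's last planned visit. The SAP nowhere says in terms that optional or non-dosing visits are included; that follows from the literal wording. The defence is fair as to intent, but it does not rescue the text. If dosing visits were meant, the sentence must say so, because the schedule contains visits that do not look like dosing visits.

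The defence is right on four stronger readings that a reader might infer:

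- *Compliance falls far below 100%, for example 8/14 = 57.1% with eight infusions.* The number of infusions is redacted, and eight is only an illustration.
- *Regimens would falsely appear to differ in compliance.* This needs different infusion counts per regimen. The regimens are redacted, and section 6.3.5 counts placebo administrations among the infusions of active participants in dose regimen 3, which may equalise the counts.
- *A participant who skips optional V2 is penalised for skipping it.* If V2 has no infusion, the literal rule counts it whether or not the participant attends, so the score is the same. Counting missed infusion visits is itself proper.
- *V10 and V13 are non-dosing because no efficacy scale is scheduled there.* Table 19 schedules safety laboratory, PK and PD samples at both visits. The absence of efficacy scales says nothing about dosing.

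It is also true that compliance is not the only record of delivery. The same section summarises treatment duration, number of infusions, dose at the first and later infusions and cumulative dose, and Listings 16.2.5.1 and 16.2.5.2 show exposure by visit and by participant.

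**Conclusion.** The inconsistency is real. Section 6.3.5 defines the denominator in doses and then instructs that it be computed in visits. Read literally, a fully dosed completer scores about 86% if V2 and V14 carry no infusion, and about 93% if only one of them carries none. Both figures rest on 14 planned visits and on an inference from the visible schedule about which visits are non-dosing; the redacted dosing row would settle it. The rule gives the right answer only if all 14 visits, including the optional one and the end-of-treatment one, are dosing visits.

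The consequence is small. It is confined to the descriptive compliance figure in Table 14.1.18 and its listing. Section 4.1 sets no compliance threshold for any analysis set, and no efficacy, safety or PK/PD analysis uses the figure. The documents do not support a claim of distortion between regimens. Severity: minor.

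**What to change.** Replace the practical sentence in section 6.3.5 with:

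*The denominator is the number of visits at which an IMP infusion (active or masking placebo) is scheduled for the participant's regimen, attended or missed, up to V14 or the early treatment discontinuation visit. Visits without a scheduled infusion are not counted.*

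Add that masking placebo infusions also count in the numerator. The existing sentence on dose regimen 3 covers the dose-related parameters but does not name compliance.

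The cost is one or two sentences in the SAP and a re-run of Table 14.1.18 and the compliance listing. No new data are needed. If the programs already count dosing visits only, the change brings the text into line with them and no result moves.
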